#### **11.9. Prior to Discharge or 7 Days Post-Procedure (Whichever Comes First)**

Subjects must be evaluated prior to discharge or 7 days post-procedure (whichever comes first) based on the assessments below. The REPRISE III eCRFs identify the specific data points to be collected.

- Weight and height
- NYHA classification
- Neurological physical examination, which must be performed by a neurologist, neurology fellow, neurology physician assistant, or neurology nurse practitioner; assessors should be independent (not involved with the care of study subjects).
- NIHSS, which must be performed by a neurology professional or certified personnel (external certification); assessors should be independent (not involved with the care of study subjects).
- Modified Rankin Scale score, which must be performed by a neurology professional or certified personnel (external or internal certification); assessors should be independent (not involved with the care of study subjects).

- 12-lead ECG per the Core Laboratory guidelines (see study Manual of Operations) and must be forwarded for analysis.
- TTE, including assessment of effective orifice area, peak systolic and mean aortic valve gradient pressure, aortic regurgitation assessment, mitral regurgitation, LVEF, left ventricular end-diastolic and end-systolic diameter, TR jet velocity and LA volume, per the Echocardiography Core Laboratory procedure guidelines (see study Manual of Operations). All TTEs for enrolled subjects must be sent to the Echocardiography Core Laboratory for independent analyses.

**Note:** For all subjects who have a valve implanted in the aortic position during the index procedure at least 1 echocardiogram must be obtained before discharge or 7 days (whichever comes first); if multiple echocardiographic studies are performed prior to discharge and within 7 days of the procedure, the latest study performed will be used for analysis. Subjects who do not receive a transcatheter valve during the index procedure are not required to have follow-up TTE.

- Current antiplatelet and anticoagulant (if applicable) medications
- Complete adverse event (AE, SAE, SADE, UADE/USADE, ADE, and CEC events) and device deficiencies assessment (with associated treatment)

#### 11.10. *Follow-up*

All implanted subjects will be evaluated at 30 days, 6 months, 12 months, 24 months, 36 months, 48 months, and 60 months post index procedure. Subjects who do not have a study device implanted will be assessed through 1 year post procedure for safety/adverse events. Physical clinic visits or follow-up visits are scheduled for appointed times after the date of the procedure. It is important that this schedule be maintained as closely as possible for all subjects. Boston Scientific Corporation recognizes that subjects may not be able to return for all scheduled visits at precisely the date required, and therefore, a period of time in which each visit is allowed is indicated in Table 11.1-1. Visits not completed will be considered missed and recorded as protocol deviations. Visits completed outside these windows will be recorded as protocol deviations. After 6 months, visits will be scheduled on an annual basis from 1 through 5 years. Each follow-up visit must be performed by study personnel; data from the required tests and images as well as medical assessments will be recorded in source documentation and captured in the eCRFs. The determination of specified study endpoints and measurements such as valve function and CEC events will require data from images and tests as outlined in the event definitions (Table 26.2-1).

In the event that study personnel learn of a subject's hospitalization outside the study center, the center should make every effort to obtain copies of reports or results based on tests (e.g., echocardiogram) and/or procedures performed on the study subject.

**Note:** A subject who has received a study valve should not be enrolled in a clinical trial of an investigational drug/device/treatment until the subject has reached the REPRISE III primary effectiveness endpoint (1 year).

### 11.10.1.30-Day Follow-up (30±7 Days)

All enrolled subjects must be evaluated 30 days after the index procedure. During the 30-day follow-up, the following assessments must be completed. The REPRISE III eCRFs identify the specific data points to be collected.

- Weight and height
- NYHA classification
- Modified Rankin Scale score, which must be performed by a neurology professional or certified personnel (external or internal certification); assessors should be independent (not involved with the care of study subjects).
- 12-lead ECG per the Core Laboratory guidelines (see study Manual of Operations) and must be forwarded to the Core Laboratory for analysis.
- Current antiplatelet, anticoagulant (if applicable) medications
- TTE including assessment of effective orifice area, peak systolic and mean aortic valve gradient pressure, aortic regurgitation assessment, mitral regurgitation, LVEF, left ventricular end-diastolic and end-systolic diameter, TR jet velocity and LA volume. TTE must be performed per the Echocardiography Core Laboratory procedure guidelines (see study Manual of Operations). All TTEs for enrolled subjects must be sent to the Echocardiography Core Laboratory for independent analyses.

**Note:** TTE must be done for all subjects who have a valve implanted in the aortic position during the index procedure. Subjects who do not receive a transcatheter valve during the index procedure are not required to have follow-up TTE.

- Quality of Life Surveys: Kansas City Cardiomyopathy and SF-12 Quality of Life Questionnaires
- Complete adverse event (AE, SAE, SADE, UADE/USADE, ADE and CEC events) and device deficiencies assessment (with associated treatment)
- For subjects who received a permanent pacemaker related to the index procedure, pacemaker dependence and percentage of beats where the ventricles are paced via pacemaker interrogation; please see the study Manual of Operations for determining pacemaker dependency.
- For subjects enrolled in the CT Imaging Substudy of the U.S. Continued Access Study, assessment of prosthetic valve leaflet mobility using 4D CT must be performed per the CT Core Laboratory procedure guidelines (see study Manual of Operations). All 4D CT scans for subjects enrolled in the CT Imaging Substudy must be sent to the CT Core Laboratory for independent analyses.

**Note:** The CT scans will be read by the CT Core Laboratory and will not be provided to local investigators except as per below. Local reading should be done only for non-cardiac valve findings such as unexpected lung pathology. A study CT scan can be

unblinded upon investigator request based on any of the following if the event occurs within 2 weeks of the study CT scan.

- Any neurological event
- Any potential embolic event
- Any MI (ST segment elevation MI or non-ST segment elevation MI)
- Increase in aortic regurgitation to moderate or severe
- A change in echocardiographic parameters including an increase in mean gradient of >10 mmHg or a change in DVI of >0.05.

If any of the above events occurs outside of the 2-week window around the study CT scan, the investigator must not be unblinded to the core laboratory assessment of the study CT scan and instead should perform a separate CT scan if clinically indicated. If an additional CT scan is performed for clinical indications, it should be sent to the CT Core Laboratory for analysis.

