- Modified Rankin Scale (mRS) at all time points
- Health status as evaluated by Kansas City Cardiomyopathy and SF-12 Quality of Life (QOL) questionnaires at baseline; 1 and 6 months; and 1, 3, and 5 years
- Resource utilization associated with the procedure and/or follow-up.

Additionally, assessment of leaflet thickening and mobility using 4D CT will be carried out at 30 days and 1 year post index procedure for subjects in the CT Imaging Substudy of the U.S. Continued Access Study. The CT scans will be evaluated by an independent CT Core Laboratory and should be blinded to local investigators for cardiac valve findings (local reading should be only for non-cardiac valve findings such as unexpected lung pathology; see Section 11.10.1 for additional information).

**Note 1:** The most current VARC definitions and endpoints available at the beginning of the trial were used.

**Note 2:** The VARC-2 safety composite at 30 days includes all-cause mortality, all stroke (disabling and non-disabling), life-threatening bleeding, acute kidney injury (Stage 2 or 3), coronary artery obstruction requiring intervention, major vascular complication, and repeat procedure for valve-related dysfunction. The VARC-2 time-related valve safety composite includes structural valve deterioration (valve-related dysfunction requiring repeat procedure [TAVR or SAVR]), prosthetic valve endocarditis, prosthetic valve thrombosis, thromboembolic events (e.g., stroke), and VARC bleeding (unless clearly unrelated to valve therapy based on investigator assessment)

**Note 3:** Clinical indications for permanent pacemaker implantation are outlined in the ACCF/AHA/HRS Guidelines for Device-Based Therapy of Cardiac Rhythm Abnormalities. Permanent pacemaker implantation should generally be performed only for accepted Class I indications.

**Note 4:** For the Lotus Valve System, repositioning may be achieved with partial or full resheathing of the valve; the proportion of subjects with partial valve resheathing and full valve resheathing will be determined.

**Note 5:** At least 1 echocardiogram must be obtained before discharge or 7 days (whichever comes first); if multiple echocardiographic studies are performed prior to discharge and within 7 days of the procedure, the latest study performed will be used for analysis.

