**Table 9.3-2: Additional Exclusion Criteria for the 4D CT Imaging Substudy of the U.S. Continued Access Study**

AEC1. Subject has eGFR <30 mL/min (chronic kidney disease stage IV or stage V).  
AEC2. Subject has atrial fibrillation that cannot be rate controlled to ventricular response rate < 60 bpm.  
AEC3. Subject is expected to undergo chronic anticoagulation therapy after the TAVR procedure.  
*Note:* Subjects treated with short-term anticoagulation post-procedure can be included in the imaging substudy; in these subjects the 30-day imaging will be performed 30 days after discontinuation of anticoagulation.

Abbreviations: AEC=additional exclusion criterion; CT=computed tomography; eGFR=estimated glomerular filtration rate; TAVR=transcatheter aortic valve replacement

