- For subjects who received a permanent pacemaker related to the index procedure, pacemaker dependence and percentage of beats where the ventricles are paced via pacemaker interrogation; please see the study Manual of Operations for determining pacemaker dependency.
- For subjects enrolled in the CT Imaging Substudy of the U.S. Continued Access Study, assessment of prosthetic valve leaflet mobility using 4D CT must be performed per the CT Core Laboratory procedure guidelines (see study Manual of Operations). The 4D CT scans done for the CT Imaging Substudy must be sent to the CT Core Laboratory for independent analyses.

**Note:** The CT scans will be read by the CT Core Laboratory and findings will not be provided to local investigators except as noted above. Local reading should be done only for non-cardiac valve findings such as unexpected lung pathology. A study CT scan can be unblinded upon investigator request based on the conditions described in Section 11.10.1 if the event occurs within 2 weeks of the study CT scan.

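### The DMC's listed cohorts omit U.S. Continued Access, and the protocol states no core-laboratory notice to the DMC, CEC or sponsor when a withheld 4D CT shows treatment-worthy thrombus in an event-free, echo-silent subject

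*Combined protocol and SAP*

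**What the plan says.** **Withholding.** Substudy subjects have a 4D CT at 30 days and at 1 year. Section 7.2 says the scans "should be blinded to local investigators for cardiac valve findings". Section 11.10.1 adds: "The CT scans will be read by the CT Core Laboratory and will not be provided to local investigators except as per below". Section 11.10.3 repeats the rule at 12 months: "findings will not be provided to local investigators except as noted above".

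**Release.** A study scan can be "unblinded upon investigator request based on any of the following if the event occurs within 2 weeks of the study CT scan". The list covers neurological events, potential embolic events, myocardial infarction, a rise in aortic regurgitation to moderate or severe, and an echo item: "A change in echocardiographic parameters including an increase in mean gradient of >10 mmHg or a change in DVI of >0.05". Outside the 2 weeks the study reading stays sealed and the investigator "instead should perform a separate CT scan if clinically indicated".

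**Who is in the substudy.** Table 9.3-2 (AEC3) excludes a candidate if "Subject is expected to undergo chronic anticoagulation therapy after the TAVR procedure". Short-term anticoagulation is allowed, but "in these subjects the 30-day imaging will be performed 30 days after discontinuation of anticoagulation".

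**Core laboratory.** Section 13.3.2 and note u of Table 11.1-1 send scans to the CT Core Laboratory for evaluation. Neither names anyone to whom a finding is passed on.

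**Committees.** Section 22.1.2 gives the DMC oversight of AEs and SAEs in the roll-in, randomized, Lotus 21 mm, LOTUS Edge, and 29 mm roll-in and registry cohorts. U.S. Continued Access is not listed. Section 8.3 promises continuing safety monitoring for the whole trial under Section 22.1, and Section 19.2 counts DMC assessment among the risk mitigations.

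**The concern.** Withholding readings of reduced leaflet motion from sites is a reasonable design. Section 4.1.1 describes the finding as mainly asymptomatic and without a definitive link to symptoms, and the substudy exists to learn its prevalence and any relation to events.

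Thrombus large enough to treat is a different matter. Table 26.2-1 lets a thrombus on or near the valve count as valve thrombosis if it blocks part of the flow path, impairs valve function, or is big enough to call for treatment. The third limb needs no symptom and no gradient change, so an imaging finding could satisfy it. Valve thrombosis is also a CEC-adjudicated event.

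Substudy subjects are selected for having no expected chronic anticoagulation, and Section 4.1.1 says leaflet motion could be restored with anticoagulation. A trial body might therefore hold a reading that calls for treatment while the stated procedures take it to nobody who could act. The committee best placed to receive it without unblinding sites does not list this cohort in its remit.

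**Working it through.** **1. DMC scope.** Planned numbers from Section 8.3, counting the LOTUS Edge registry at its stated minimum of 50:

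- Cohorts listed in Section 22.1.2: 120 + 912 + 20 + 50 + 20 + 20 = 1142.
- Adding U.S. Continued Access: 1142 + 1000 = 2142, which reproduces the protocol's total.
- Share not listed: 1000 / 2142 = 46.7%.
- CT substudy: about 200 / 1000 = 20% of that cohort, at two scans each, so about 400 scans.

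**2. Where a reading can go.**

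| Situation | Stated path |
|---|---|
| Listed event within 2 weeks of the scan | Investigator may request the study reading |
| Listed event outside 2 weeks | Separate CT if clinically indicated; study reading stays sealed |
| Other reported event | Section 22.1: sponsor or designee gathers dossier material, including from core laboratories |
| No event and no echo change | None stated |

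Other provisions do not fill the last row:

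- Section 22.1 starts its collection from a reported event.
- Section 22.1.1 has the CEC review what investigators report.
- Note t of Table 11.1-1 requires CEC events to be reported for all enrolled subjects, but someone must first recognise one.
- Section 11.10 says CEC events will need imaging data, without naming a route.
- Section 17.2 binds the investigator, who does not have the reading.
- Section 20 works through a revised consent form.
- Section 21.5 starts from a serious event, an unanticipated effect or a device deficiency.

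**3. When a scheduled TTE can release the first study scan.** Let T be the day of the 30-day TTE (window 23 to 37) and D the day short-term anticoagulation stops, so the first CT falls on day D + 30.

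- Undelayed CT: both lie in days 23 to 37, so the largest gap is 37 − 23 = 14 days. The TTE always qualifies.
- Delayed CT: gap = D + 30 − T, which exceeds 14 when D > T − 16. That is D > 7 for T = 23, D > 14 for T = 30, and D > 21 for T = 37.
- The 6-month TTE window opens on day 150. The gap 150 − (D + 30) exceeds 14 when D ≤ 105.
- So for D = 22 to 105 no in-window 30-day or 6-month TTE lies within 14 days of that CT. End checks: D = 22 gives 52 − 37 = 15; D = 105 gives 150 − 135 = 15.
- With an assumed ±7-day CT tolerance: D + 23 − 37 > 14 gives D ≥ 29, and D + 37 < 136 gives D ≤ 98.
- Example: stopping on day 30 puts the CT on day 60, between 60 − 37 = 23 and 60 − 23 = 37 days after the 30-day TTE.
- At 12 months (days 335 to 395) TTE and CT can be 60 days apart, and no interval between them is set.

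This reads the imaging that AEC3 delays as the CT alone. If the TTE moves with it, the 30-day part of the timing gap closes.

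**The case against.** **The timing result is easy to over-read.** A reader might infer that thrombus goes undetected in subjects who stop anticoagulation between days 22 and 105. The documents do not support that. Section 11.10.1 directs the investigator to a separate clinical CT when a listed change falls outside the window, so an echo change can still be pursued. An unscheduled echo near the study scan could also release it. The protocol gives neither a duration for short-term anticoagulation nor the number of subjects on it. The calculation shows only when a scheduled TTE cannot release the study scan.

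**The residual case is narrow.** Thrombus that impedes flow or function would often trip the wide, open-ended echo trigger. What remains is a treatment judgement on an echo-silent scan, and the stated CT assessment is of leaflet thickening and mobility, not a thrombosis diagnosis.

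**The protocol's silence is not proof.** A reader might conclude that the trial has no alert route. Committee procedures sit in charters, and imaging procedures in core-laboratory guidelines and the Manual of Operations. None of these is available here. Only local investigators are blinded, so nothing stated forbids the laboratory from telling the sponsor or the DMC.

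**The DMC omission may be deliberate.** The change log (Table 27.1-6) shows the cohort list entering in the revision that created U.S. Continued Access. That cohort is single-arm and descriptive (Section 12.1). The 46.7% therefore does not mean that nearly half the subjects lack safety oversight: their events are still reported to the sponsor, and Section 22.1.2 also has a general sentence on accumulating safety data. Nor would adding the cohort name alone route a CT reading.

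**What stands.** The explicit list omits the cohort without a stated reason, despite Sections 8.3 and 19.2, and no text starts a notice from the core laboratory.

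**Conclusion.** The point holds as a cheap, minor improvement with two linked parts: the DMC's listed remit excludes the substudy's parent cohort, and one kind of reading has no stated onward path. The figure for DMC scope is a planned maximum and says nothing about how often CT would show treatable thrombus.

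That frequency cannot be estimated. The documents give no CT prevalence. The full-cohort REPRISE II count, 3 thromboses in 249 subjects by 1 year (1.2%), is a reported-event rate. Those cases resolved with anticoagulants (Section 4.1.3), which shows that treatment worked once a case was found, not that delay harms.

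The conclusion rests on the protocol text alone and would weaken if a charter or laboratory guideline already holds an alert.

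**What to change.** - **Section 22.1.2:** add U.S. Continued Access to the DMC's cohorts, or at minimum the CT substudy.
- **Sections 11.10.1 and 11.10.3:** have the CT Core Laboratory promptly notify the DMC of any scan with thrombus it considers large enough to warrant treatment. Reduced leaflet motion alone would not trigger a notice. The DMC may recommend unblinding that subject's site; other sites stay blinded. If an existing charter or guideline already does this, cite it there.
- **Reporting:** show CT-detected cases separately from CEC-adjudicated valve thrombosis, so that surveillance by CT does not inflate the event rate.

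The cost is one cohort name, a data-transfer line and DMC charter wording, using bodies that already exist. The downside is modest extra DMC work and a few possible unblindings, which would slightly weaken the natural-history reading.

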#### 11.10.2. 6-Month (180±30 Days) Follow-up

All implanted subjects must be evaluated at 6 months after the index procedure. During the 6-month follow-up, the following assessments must be completed. The REPRISE III eCRFs identify the specific data points to be collected.

- Weight and height
- NYHA classification
- Modified Rankin Scale score, which must be performed by a neurology professional or certified personnel (external or internal certification); assessors should be independent (not involved with the care of study subjects).
- 12-lead ECG per the Core Laboratory guidelines (see study Manual of Operations) and must be forwarded for analysis
- Current antiplatelet, anticoagulant (if applicable) medications
- TTE, including assessment of effective orifice area, peak systolic and mean aortic valve gradient pressure, aortic regurgitation assessment, mitral regurgitation, LVEF, left ventricular end-diastolic and end-systolic diameter, TR jet velocity and LA volume, per the Echocardiography Core Laboratory procedure guidelines (see study Manual of Operations). It must be sent to the Core Laboratory for independent analysis.  
**Note:** TTE must be done for all subjects who have a valve implanted in the aortic position during the index procedure. Subjects who do not receive a transcatheter valve during the index procedure are not required to have follow-up TTE.
- Complete adverse event (AE, SAE, SADE, UADE/USADE, ADE and CEC events) and device deficiencies assessment (with associated treatment)
- Quality of Life Surveys: Kansas City Cardiomyopathy and SF-12 Quality of Life Questionnaires

### 11.10.3.12-Month (365±30 Days) Follow-up

All implanted subjects must be evaluated at 12 months after the index procedure. During the 12-month follow-up, the following assessments must be completed. The REPRISE III eCRFs identify the specific data points to be collected.

- Physical examination including weight and height
- NYHA classification
- Modified Rankin Scale score, which must be performed by a neurology professional or certified personnel (external or internal certification); assessors should be independent (not involved with the care of study subjects).
- Neurological physical examination, which must be performed by a neurologist, neurology fellow, neurology physician assistant, or neurology nurse practitioner (see Table 11.1-1); assessors should be independent (not involved with the care of study subjects).
- NIHSS, which must be performed by a neurology professional or certified personnel (external certification); assessors should be independent (not involved with the care of study subjects).
- Gait speed to walk 5 meters
- Rotational x-ray angiography performed on subjects who received the Lotus Valve to assess for structural valve frame integrity per the Imaging Core Laboratory procedure guidelines (see study Manual of Operations). It must be forwarded to the Core Laboratory for analysis.
- 12-lead ECG per the Core Laboratory Guidelines (see study Manual of Operations) and must be forwarded for analysis
- Current antiplatelet and anticoagulant (if applicable) medications
- TTE, including assessment of effective orifice area, peak systolic and mean aortic valve gradient pressure, aortic regurgitation assessment, mitral regurgitation, LVEF, left ventricular end-diastolic and end-systolic diameter, TR jet velocity and LA volume, per the Echocardiography Core Laboratory procedure guidelines (see study Manual of Operations). It must be forwarded to the Core Laboratory for independent analysis.  
**Note:** TTE must be done for all subjects who have a valve implanted in the aortic position during the index procedure. Subjects who do not receive a transcatheter valve during the index procedure are not required to have follow-up TTE.
- Complete adverse event (AE, SAE, SADE, UADE/USADE, ADE and CEC events) and device deficiencies assessment (with associated treatment)
- Quality of Life Surveys: Kansas City Cardiomyopathy and SF-12 Quality of Life Questionnaires

- For subjects who received a permanent pacemaker related to the index procedure, pacemaker dependence and percentage of beats where the ventricles are paced via pacemaker interrogation; please see the study Manual of Operations for determining pacemaker dependency.
- For subjects enrolled in the CT Imaging Substudy of the U.S. Continued Access Study, assessment of prosthetic valve leaflet mobility using 4D CT must be performed per the CT Core Laboratory procedure guidelines (see study Manual of Operations). The 4D CT scans done for the CT Imaging Substudy must be sent to the CT Core Laboratory for independent analyses.

**Note:** The CT scans will be read by the CT Core Laboratory and findings will not be provided to local investigators except as noted above. Local reading should be done only for non-cardiac valve findings such as unexpected lung pathology. A study CT scan can be unblinded upon investigator request based on the conditions described in Section 11.10.1 if the event occurs within 2 weeks of the study CT scan.

